10.5.1 Patient Reported Outcomes

The PRO instruments to be measured in this study are described below. These measures will be administered in this study at 3 timepoints: Screening or Baseline Visit, 6-month visit, and Completion/Termination Visit, whereas the EQ-5D, Patient Activity Level, and Health Resource Use will be measured at each study visit before study specific procedures are started. Note that due to the unavailability of linguistically validated translations of certain PRO measures in certain countries, some of these questionnaires may not be administered in all countries participating in this study. In addition, subjects who are younger than the minimal age limit required for these assessments will not be required to complete the assessment.

1. **Haemo-SYM Questionnaire** – This is a self-administered, validated questionnaire designed to assess symptom severity in subjects with hemophilia. This measure contains 17 items and includes 2 domains: Bleeds and Pain. Scores for each of these 2 domains can be calculated, with higher scores indicating more severe symptoms. This questionnaire will be administered only to subjects \geq 18 years of age.
2. **Short Form-36 (SF-36)** – The SF-36 is a self-administered, validated questionnaire designed to measure generic HRQoL. This 36-item questionnaire measures 8 domains, including: Physical functioning, Role-physical, Bodily pain, General health, Vitality, Social functioning, Role emotional, and Mental health.

Two summary scores can be calculated, the Physical Component Score, and the Mental Component Score. Additionally, scores can be calculated for each of the 8 domains. Higher scores indicate better health status. This questionnaire will be administered only to subjects ≥ 14 years of age.

3. **EQ-5D Questionnaire** – The EQ-5D is a self-administered, standardized measure of health status that provides a generic measure of health for clinical and economic appraisal consisting of the following 5 dimensions: mobility, self-care, usual activities, pain/discomfort, and anxiety/depression each with 3 levels. There is an additional EQ visual analog scale to record how good or bad their health state is.
4. **Patient Activity Level**
Subjects will also be asked to estimate their activity levels. This will consist of a few questions asking subjects to rate their current level of activity. These data will be collected for all age groups.

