5.10 Common Calculations

For quantitative measurements, change from baseline is calculated as:

Change from Baseline at Visit X = Test Value at Visit X – Baseline Value

Change from pre-infusion is calculated as:

Change from pre-infusion at Visit X = Test Value at Visit X post-infusion – Test Value at Visit X pre-infusion

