7.2 Analysis of Secondary Efficacy Outcome Measures

The following secondary efficacy outcome measures are discussed in Section 7.1.2:
Bleeding Episodes:

- Total, Spontaneous, and Injury Related (Traumatic) ABR, and Spontaneous AJBR.
- Overall hemostatic efficacy rating at 8 hours (± 1 hour) after initiation of BAX 855 infusion for the treatment of the bleed as well as at the resolution of the bleed.
- Number of BAX 855 infusions needed for the treatment of bleeding episodes.
- Intra-, post- and perioperative hemostatic efficacy in case of surgery.
- Intra- and postoperative blood loss in case of surgery.

The following are the other secondary efficacy measures that are discussed in this section:

- HJHS questionnaire.
- Haemo-SYM questionnaire.
- Physical domain and component scores of the SF-36 questionnaire.
- EQ-5D questionnaire.
- Healthcare resource utilization (as recorded in the subject diaries).
- Subject physical activity levels.
- The total weight-adjusted consumption of BAX 855 for each treatment arm.

Subject listings will be presented for the following items using the SAS:

- HJHS questionnaire.
- Haemo-SYM questionnaire
- SF-36 questionnaire.
- EQ-5D questionnaire.
- Health resource usage and events.
- Physical activity.

Summary tables containing descriptive statistics and comparisons, using the Wilcoxon signed rank and Mann-Whitney U tests, will be presented on the following items using the FAS:

- The HJHS questionnaire.
- The Haemo-SYM questionnaire.
- The SF-36 questionnaire.
- The EQ-5D questionnaire.
- Health Resource Use.

A summary table containing descriptive statistics only of subject physical activity will also be presented. The summary tables should be presented by age group.

The following information item is obtained from the eCRF:

- Haemophilia joint health score (*Joint score [HJHS] eCRF panel*).

The following information items are obtained from the ERT third party vendor diary data:

- Haemo-SYM item responses and scores.
- SF-36 item responses and scores.
- EQ-5D item responses and scores.
- Health resource utilization.
- Physical activity records.

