7.2.1 Haemophilia Joint Health Score (HJHS) Questionnaire

The HJHS is a questionnaire based assessment of the physical structure and function of the joints in subjects with haemophilia. Each joint is assessed in terms of swelling, muscle atrophy, crepitus on motion, extension, flexion loss, joint pain and joint strength. A global gait score is separately assessed, ranging from '0' (indicating all skills are within normal limits), to '4' (indicating that no skills are within normal limits). The global gait score combined with the joint scores, forms the HJHS total score. A lower HJHS score indicates a better condition of the joint. Therefore, negative change scores indicate that symptoms have improved.

The questions in the HJHS questionnaire are scored as set out in Table 1:

Table 1 HJHS Questionnaire Item Scores

Item	Score
Swelling	No Swelling: 0
	Mild: 1

Item	Score
	Moderate: 2
	Severe: 3
	Non evaluable: No score
Duration (Swelling)	No Swelling or < 6 months: 0
	≥ 6 months: 1
	Non evaluable: No score
Muscle Atrophy	None: 0
	Mild: 1
	Severe: 2
	Non evaluable: No score
Crepitus on Motion	None: 0
	Mild: 1
	Severe: 2
	Non evaluable: No score
Flexion Loss	< 5 degrees: 0
	5 degrees to 10 degrees: 1
	11 degrees to 20 degrees: 2
	> 20 degrees: 3
	Non evaluable: No score
Extension Loss	< 5 degrees: 0
	5 degrees to 10 degrees: 1
	11 degrees to 20 degrees: 2
	> 20 degrees: 3
	Non evaluable: No score
Joint Pain	No pain through active range of motion: 0
	No pain through active range; only pain on gentle overpressure or palpitation: 1
	Pain through active range: 2
	Non evaluable: No score
Strength	Holds test position against gravity with maximum resistance (gr.5): 0
	Holds test position against gravity with moderate resistance (but breaks with maximum resistance (gr.4): 1
	Holds test position with minimal resistance (gr.3+) or holds test position against gravity (gr.3): 2
	Able to partially complete ROM against gravity (gr.3-/2+), or able to move through ROM gravity eliminated (gr.2-): 3
	Trace (gr.1) or no muscle contraction (gr.0): 4
	Non evaluable: No score
Global Gait Score	All skills are within normal limits: 0
	One skill is not within normal limits: 1
	Two skills are not within normal limits: 2
	Three skills are not within normal limits: 3
	No skills are within normal limits: 4
	Non evaluable: No score

The following derivations will be made based of the eCRF reported results:

- The joint totals (per assessment) are calculated as:

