$$\text{Joint Totals} = \sum \text{Individual item scores per joint within a subject}$$

- The sum of joint totals (per assessment) is calculated as:

$$\text{Sum of Joint Totals} = \sum \text{Joint totals within a subject}$$

- The HJHS total score is calculated as:

$$\text{HJHS Total Score} = \text{Sum of Joint Totals} + \text{Global Gait Score}$$

A Wilcoxon Signed Rank test for paired samples will be used to assess the within treatment arm change in HJHS total score between baseline and completion for any significant statistical differences. The following SAS[®] code can be used:

```
Proc Univariate Data = <Dataset>;  
  Var <Change>;  
  By <Treatment>  
  ODS Output TestsForLocation = <Outdata>  
  (WHERE = (test = 'Signed Rank'));  
Run;  
Quit;
```

Where <Dataset> refers to the input dataset, <Change> the change from baseline at the completion visit, <Treatment> then assigned treatment arm and <Outdata> the resulting dataset from the procedure containing the inferential statistics for presentation.

A Mann-Whitney U test will be used to assess the between treatment arm change in HJHS total score from baseline to completion for any significant statistical differences. The exact p-value should be selected and presented. The following SAS[®] code can be used:

```
Proc NPAR1WAY Data = <Dataset> Wilcoxon;  
  Class <Treatment>;  
  Var <Change>;  
  exact Wilcoxon /MC;
```

```
ODS Output Wilcoxonetest = <Outdata>;  
Run;  
Quit;
```

Where <Dataset> refers to the input dataset, <Treatment> the assigned treatment arm, <Change> the change from baseline at the completion visit and <Outdataset> the resulting dataset from the procedure containing the inferential statistics for presentation.

Statistical significant differences are present if a p-value of <0.05 is obtained.

Values for the Wilcoxon Rank Sum and Mann-Whitney U tests will be selected using the distribution based, $\frac{1}{2}$ standard deviation minimal important difference (MID) threshold as promoted by Norman et al³. Change in subject HJHS total score from baseline at the completion visit $> \frac{1}{2}$ SD of the baseline total scores across all subjects should be considered a MID and will be included in both the Wilcoxon Rank sum test as well as the Mann-Whitney U test.

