7.2.2 Haemophilia Symptom (Haemo-SYM) Questionnaire

The haemophilia symptom questionnaire (Haemo-Sym) is a self reported instrument of measuring symptom severity in patients with haemophilia and has two subscales: pain and bleeds. Lower Haemo-SYM scores indicate fewer symptoms. Therefore, negative change scores indicate that symptoms have improved.

The questions in the Haemo-Sym questionnaire are assigned to the subscales of pain and bleeds as set out in Table 2:

Table 2 Haemo-Sym Questionnaire Subscales

Question (Severity of...)	Subscale
Spontaneous bleeding in my joints (unrelated to injury or activity)	Bleed
Spontaneous bleeding in my muscles (unrelated to injury or activity)	Bleed
Prolonged bleeding after injury in spite of treatment	Bleed

Question (Severity of...)	Subscale
Intense pain because of bleeding event	Bleed
Pain because of swelling in my joints	Pain
Joint pain due to active bleed	Bleed
Bleeding during personal hygiene routine (during shaving, tooth brushing or flossing)	Bleed
Pain because of climbing stairs	Pain
Pain upon waking in the morning	Pain
Constant pain	Pain
Pain because of active arthritis	Pain
Pain in my muscles	Pain
Pain that needs medication	Pain
Joint sensitivity to weather conditions	Pain
Reduced range of joint movement	Pain
Joint deformity	Pain
Sleep disturbance because of pain or bleeds	Pain
Blood in my urine	None
Nose bleeds	None

Results are assigned scores as follows:

- Absent = 0.
- Very mild = 1.
- Mild = 2.
- Moderate = 3.
- Severe = 4.
- Very severe = 5.

The following derivations will be made based of the subject diary reported results:

- The score for each subscale is determined only if at least 50% of the results in that subscale is available. The score should be determined as:

$$Score = \frac{MeanScore}{5} \times 100$$

where MeanScore is the mean of the available results in the particular subscale. If less than 50% of the results in a subscale is available, then no score will be calculated for that subscale.

- The total score for the Haemo-Sym questionnaire should be determined as the mean score of the two subscales should both subscale scores be available.

Within treatment arm change and between treatment arm change in Haemo-SYM total score as well as bleed and pain severity between baseline and completion will be tested for any statistical significant differences in a similar manner as described in Section 7.2.1: Haemophilia Joint Health Score (HJHS) Questionnaire.

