 &+ W_{PD3} \times PD3 + W_{AD2} \times AD2 + W_{AD3} \times AD3
 \end{aligned}$$

where the variables above are defined in Table 5 and Table 8 .

Table 8 EQ-5D TTO Value Sets (Excluding USA)

Weight Name	Denmark	Germany	Japan	Netherlands	Spain	UK	Zimbabwe
W_FH	1	1	1	1	1	1	1
W_N2	-0.114	-0.001	-0.152	-0.071	-0.024	-0.081	-0.100
W_N3	0	-0.323	0	-0.234	-0.291	-0.269	0
W_MO2	-0.053	-0.099	-0.075	-0.036	-0.106	-0.069	-0.056
W_MO3	-0.411	-0.327	-0.418	-0.161	-0.43	-0.314	-0.204
W_SC2	-0.063	-0.087	-0.054	-0.082	-0.134	-0.104	-0.092
W_SC3	-0.192	-0.174	-0.102	-0.152	-0.309	-0.214	-0.231
W_UA2	-0.048	0	-0.044	-0.032	-0.071	-0.036	-0.043
W_UA3	-0.144	0	-0.133	-0.057	-0.195	-0.094	-0.135
W_PD2	-0.062	-0.112	-0.08	-0.086	-0.089	-0.123	-0.067
W_PD3	-0.396	-0.315	-0.194	-0.329	-0.261	-0.386	-0.302
W_AD2	-0.068	0	-0.063	-0.124	-0.062	-0.071	-0.046
W_AD3	-0.367	-0.065	-0.112	-0.325	-0.144	-0.236	-0.173

- For USA, the utility total score using the “TTO” value set can be derived as:

$$Utility\ Total\ Score = W_{FH} + W_{MO2} \times MO2 + W_{MO3} \times MO3 + W_{SC2} \times SC2 + W_{SC3} \times SC3 + W_{UA2} \times UA2 + W_{UA3} \times UA3 + W_{PD2} \times PD2 + W_{PD3} \times PD3 + W_{AD2} \times AD2 + W_{AD3} \times AD3 + W_{D1} \times D1 + W_{I2_SQ} \times I2_SQ + W_{I3} \times I3 + W_{I3_SQ} \times I3_SQ$$

where the variables above are defined in Table 5, Table 9 and Table 10:

Table 9 EQ-5D USA Additional Variable Definitions

Variable Description	Variable	Possible Values	Weight
Number of movements away from full health beyond the first	D1	0, 1, 2, 3, 4	$W_{D1} = 0.140$
Square if I2 (I2 = Number of dimensions at level 2 beyond the first)	I2_SQ	0, 1, 4, 9, 16	$W_{I2_SQ} = -0.011$
Number of dimensions at level 3 beyond the first	I3	0, 1, 2, 3, 4	$W_{I3} = 0.122$
Square if I3	I3_SQ	0, 1, 4, 9, 16	$W_{I3_SQ} = 0.015$

Table 10 EQ-5D VAS Values for USA

Weight Name	USA
W_FH	1
W_MO2	-0.146
W_MO3	-0.558
W_SC2	-0.175
W_SC3	-0.471
W_UA2	-0.14
W_UA3	-0.374
W_PD2	-0.173
W_PD3	-0.537
W_AD2	-0.156
W_AD3	-0.45

Within treatment arm change and between treatment arm change in EQ-5D utility total score as well as the VAS score between baseline and completion will be tested for any statistical significant differences in a similar manner as described in Section 7.2.1: Haemophilia Joint Health Score (HJHS) Questionnaire.

The following EQ-5D total scores form part of both the secondary and exploratory efficacy outcomes:

- Utility total score.
- VAS score.

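### The HJHS, Haemo-SYM, SF-36 and EQ-5D change tests keep only subjects whose own change exceeds half a baseline SD, which selects subjects on the outcome being tested

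*SAP*

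**What the plan says.** SAP 7.2 plans "comparisons, using the Wilcoxon signed rank and Mann-Whitney U tests, will be presented on the following items using the FAS", and the list names HJHS, Haemo-SYM, SF-36, EQ-5D and health resource use. SAP 7.2.1 then describes a within-arm signed-rank test and a between-arm Mann-Whitney test of the change from baseline to completion, and closes with a selection step: "Values for the Wilcoxon Rank Sum and Mann-Whitney U tests will be selected using the distribution based" half-SD MID threshold. A change in HJHS total greater than half the SD of the baseline totals over all subjects "should be considered a MID and will be included in both the Wilcoxon Rank sum test as well as the Mann-Whitney U test".

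The later sections refer back to this one. SAP 7.2.2 says Haemo-SYM changes "will be tested for any statistical significant differences in a similar manner as described in Section 7.2.1". SAP 7.2.3 (SF-36) and 7.2.7 (health resource use) carry the same cross-reference, as does 7.2.4, where the "change in EQ-5D utility total score as well as the VAS score between baseline and completion will be tested". SAP 7.2.5 makes physical activity descriptive only, so the rule does not reach it.

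Three other places matter:

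- **Sign of change.** SAP 5.10 defines "Change from Baseline at Visit X = Test Value at Visit X – Baseline Value". For HJHS, "Therefore, negative change scores indicate that symptoms have improved", and SAP 7.2.2 says the same of Haemo-SYM. For SF-36, Protocol 10.5.1 says "Higher scores indicate better health status".
- **Protocol method.** Protocol 14.4.2 and 14.4.3 name an MID threshold alongside the two rank tests for the patient-reported outcomes, without saying that anyone is left out. Protocol 14.4.2 lists HJHS among the outcomes to be described, not tested.
- **Declared changes.** SAP 5.8 mentions neither the selection step nor the added HJHS tests.

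**The concern.** An MID normally helps to interpret a result. Here it controls entry to the test, and it is applied to the variable under test. The retained groups are defined by a post-randomisation outcome, so the Mann-Whitney test compares two self-selected subsets.

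The threshold also has no direction. With change defined as visit minus baseline, the wording as it stands keeps only rises above half an SD. On HJHS and Haemo-SYM those are subjects who got worse; on SF-36 and EQ-5D they are subjects who got better. A signed-rank test on values that are all positive rejects almost automatically once a few are retained.

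The SF-36 physical scores are a named secondary outcome with their own between-arm objective. At stake are within-arm p-values that may report change where there is none, and a between-arm test that may miss a real difference.

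**Working it through.** **Sample size used.** The documents give no sample size for these tests, so I take the 48 evaluable per arm from SAP 2.3. That figure reproduces: for 40% against 70%, two-sided 5% and 80% power, the continuity-corrected formula gives 49 per arm, and the exact power of the continuity-corrected chi-square test at 48 is 0.8005.

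**Assumptions not in the documents.** Normal scores with equal variance at both visits; baseline-completion correlation r from 0.5 to 0.95; no true change for the error rates; an arm difference of 0.6 SD of change for power.

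**Step 1: the signed-rank p-value when all values are positive.** With k retained values of one sign, the exact two-sided p is 2/2^k. For k = 5 it is 2/32 = 0.0625; for k = 6 it is 2/64 = 0.031. Six retained subjects give p < 0.05 whatever the treatment does. This step needs none of the assumptions above.

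**Step 2: how many are retained.** The SD of change is sqrt(2(1 − r)) baseline SDs, so P(change > 0.5 SD) = 1 − Φ(0.5/sqrt(2(1 − r))). At r = 0.8 this is 1 − Φ(0.5/0.632) = 0.215, or 48 × 0.215 = 10.3 subjects per arm. The absolute rule discards 1 − 2 × 0.215 = 57%.

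**Step 3: false within-arm significance, signed reading.** This is the binomial probability of retaining at least six of 48.

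| r | P(change > 0.5 SD) | Kept of 48, signed | P(k ≥ 6) | Discarded, absolute |
|---|---|---|---|---|
| 0.5 | 0.309 | 14.8 | 0.999 | 38% |
| 0.7 | 0.259 | 12.4 | 0.993 | 48% |
| 0.8 | 0.215 | 10.3 | 0.962 | 57% |
| 0.9 | 0.132 | 6.3 | 0.619 | 74% |
| 0.95 | 0.057 | 2.7 | 0.054 | 89% |

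With 58 per arm, P(k ≥ 6) is 1.000, 0.999, 0.992, 0.793 and 0.111.

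**Step 4: simulation.** 3,000 trials per setting at 48 per arm, with the threshold set at half the pooled sample baseline SD. A fall is benefit on HJHS and Haemo-SYM; a rise is benefit on SF-36.

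| r | 0.5 | 0.7 | 0.8 | 0.9 | 0.95 |
|---|---|---|---|---|---|
| Within-arm false rejection, signed | 99.9% | 99.2% | 96.2% | 61.5% | 7.2% |
| Within-arm false rejection, absolute | 5.0% | 5.9% | 4.8% | 3.9% | 1.7% |
| Between-arm type I error, signed | 4.6% | 3.8% | 4.7% | 3.5% | 0.6% |
| Between-arm type I error, absolute | 4.8% | 5.7% | 5.5% | 4.7% | 2.8% |
| Power, all subjects (fall) | 81.4% | 80.2% | 81.1% | 78.1% | 80.8% |
| Power, signed, fall | 8.1% | 6.0% | 4.6% | 1.6% | 0.1% |
| Power, signed, rise | 15.0% | 12.1% | 10.7% | 6.6% | 3.3% |
| Power, absolute (fall) | 77.1% | 71.7% | 69.4% | 52.6% | 27.3% |

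Monte Carlo error near 5% is about 0.4 percentage points.

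**Step 5: size of the observed difference.** A separate simulation (2,000 trials per setting) set the SD of change at 0.7 baseline SD. A true arm difference of 0.42 baseline SD showed as 0.71 among subjects kept by the absolute rule and 0.12 among those kept by the signed rule.

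**The case against.** The strongest reply is that the alarming figures come from the less plausible reading. An MID is a size of change, the SAP knows that falling scores are improvement on HJHS and Haemo-SYM, and the missing absolute-value sign is probably a drafting gap. On the absolute reading neither test's error rate is inflated, provided change is symmetric under the null. That is fair, and the literal reading should be treated as an ambiguity and not as the sponsor's intent. It does not rescue the rule, because the absolute reading still discards 38% to 89% of subjects, costs power and exaggerates the observed difference.

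Second, the protocol already ties an MID threshold to these tests for SF-36, Haemo-SYM and EQ-5D, so the SAP may only be filling in a method left open. This stands in part: the threshold is not new. Excluding subjects with it is new, and so is testing HJHS.

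Third, naming the Full Analysis Set does not by itself forbid a further rule on which values enter. The sample code has no filter, but its input dataset is a placeholder, so selection could happen upstream. Both points are correct. They mean the SAP does not settle what will be programmed. Only HJHS carries the rule in words; the other instruments get it by cross-reference.

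Fourth, the sizes are generic. HJHS sums small integer items and EQ-5D utility is capped at 1, so normality is doubtful. Protocol 10.5.1 limits Haemo-SYM to age 18 and over and SF-36 to age 14 and over, so fewer than 48 may contribute. With an illustrative 30 per arm, P(k ≥ 6) is 94%, 83%, 65%, 20% and 0.6% across the same correlations. The size changes; the fault does not.

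**Conclusion.** The concern holds. As written, SAP 7.2.1 chooses test subjects by the outcome being tested, and neither reading gives a sound comparison of the randomised arms on the Full Analysis Set.

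- **Literal reading:** within-arm p-values mean little unless very few subjects pass the threshold (62% to 99.9% false significance for r up to 0.9). They point to worsening on HJHS and Haemo-SYM and to improvement on SF-36. Between-arm power is at most about 15%.
- **Absolute reading:** the damage is a moderate to large loss of power, an exaggerated arm difference and a non-randomised subset.

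Between-arm type I error is not inflated under either reading. Confidence is high on the text and on the 2/2^k result. The percentages depend on the assumed correlations, normality, 48 per arm and the 0.6 SD effect. The affected endpoints are secondary or exploratory, and the primary endpoint and ABR analyses are untouched. This should be corrected before the analysis is run.

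**What to change.** 1. Delete the selection rule from SAP 7.2.1. Run the signed-rank and Mann-Whitney tests on the change scores of all Full Analysis Set subjects with both a baseline and a completion value, and say so explicitly. Apply the same wording to Haemo-SYM, SF-36, EQ-5D and health resource use.
2. Report the MID separately: per arm, the proportion improving and the proportion worsening by at least half a baseline SD. Define direction for each instrument: negative is better for HJHS and Haemo-SYM, positive is better for SF-36 and EQ-5D. State a direction for health resource use if it is included.
3. In the same paragraph, replace the rank-sum name with signed-rank; the rank-sum test is the Mann-Whitney test under another name.
4. Record in SAP 5.8 how the MID wording of Protocol 14.4.2 and 14.4.3 is implemented, and that HJHS, descriptive in the protocol, is now tested.

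The cost is minor: a reworded paragraph, an entry in SAP 5.8 and one added responder table. No new data are needed.
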